7.1 Multiple Sclerosis

Multiple sclerosis (MS) is a chronic autoimmune, inflammatory neurological disease of the central nervous system (CNS) (Calabresi 2004, Hauser 2008). MS attacks the myelinated axons in the CNS, destroying the myelin and the axons to varying degrees (Weinshenker 1996, Olek 2011).

The course of MS is highly varied and unpredictable. In most patients, the disease is characterized initially by episodes of reversible neurological deficits, which are often followed by progressive neurological deterioration over time.

In Europe there are more than 600,000 patients estimated to be suffering from MS, with a median prevalence of 100 cases and a median incidence of 5.5 cases per 100,000 (Bezzini, 2017), and 50% of patients will need help walking within 20 years after the onset of the disease (Brown 2019).

Twice as many women are affected as men, and persons of Northern European descent appear to be at highest risk for MS (Hauser 2008, Cree 2007). The disease is diagnosed on the basis of clinical findings and supporting evidence from ancillary tests, such as magnetic resonance imaging (MRI) of the brain and examination of the cerebrospinal fluid (CSF). MS typically presents in adults 20 to 45 years of age; occasionally, it presents in childhood or late middle age (Cree 2007).

The cause of MS is unknown, but it appears to involve a combination of genetic susceptibility and a nongenetic trigger, such as a virus, metabolism, or environmental factors resulting in a self-sustaining autoimmune disorder that leads to recurrent immune attacks on the CNS (Cree 2007).

Neurologists agree that patients may be grouped into four major categories based on the course of disease (Hauser 2008, Goldenberg 2012):

- Relapsing-remitting MS: the most common form, affecting about 85% of MS patients. It
 is marked by flare-ups (relapses or exacerbations) of symptoms followed by periods of
 remission, when symptoms improve or disappear.
- Secondary progressive MS: may develops in approximately 50% of patients with relapsing-remitting disease within 20 years of disease progression (Brown 2019). For many patients, treatment with disease-modifying agents helps delay such progression. The disease course continues to worsen with or without periods of remission or leveling off of symptom severity (plateaus).
- 3. Primary progressive MS: affects approximately 10% of MS patients. Symptoms continue to worsen gradually from the beginning. There are no relapses or remissions, but there may be occasional plateaus. This form of MS is more resistant to the drugs typically used to treat the disease. Currently only ocrelizumab has been approved for the treatment of PPMS.
- 4. Progressive-relapsing MS: a rare form, affecting fewer than 5% of patients. It is progressive from the start, with intermittent flare-ups of worsening symptoms along the way. There are no periods of remission.

7.2 MAVENCLAD ® (Cladribine Tablets) 3.5 mg/kg

Recently, the number of available disease-modifying therapies for treatment of relapsing-remitting MS (RRMS) has increased (Carrithers 2014, Wingerchuk 2014). However, many patients treated with these agents continue to experience relapses and disease progression (Tsivgoulis 2015, Hadjigeorgiou 2013, Tramacere 2015); thus, new treatment options are still required. Cladribine, a synthetic deoxyadenosine analog that acts in peripheral tissues, enters the CNS and is taken up by lymphocytes and phosphorylated by deoxycytidine kinase, resulting in targeted and sustained reductions of the T and B lymphocytes that are implicated in the pathogenesis of MS (Leist 2011).

In the Phase III CLARITY study treatment with Cladribine tablets given in short courses annually for 2 years significantly improved clinical and MRI outcomes (Giovannoni 2010). Lymphopenia was the most commonly reported adverse event (AE) (Cook 2011). In CLARITY Extension, the clinical benefits of 2 years of treatment with Cladribine tablets were shown to be durable, without further active treatment (Giovannoni 2017). In the ORACLE-MS study, Cladribine tablets significantly reduced the risk of clinically definite MS in patients with a first clinical demyelinating event compared with placebo (Leist 2014), while in the ONWARD study it further reduced the ARR when co-administered with IFN- β (Montalban 2018).

7.3 Expected contribution of this study to the knowledge on Cladribine tablets in RRMS

The main aim is to study in the real world setting the effectiveness of Cladribine tablets in terms of ARR and disability progression, in patients that switch from a first line drug (Interferons, Glatiramer Acetate, Teriflunomide, DMF).

In the CLARITY study approximately. 30% of participants were pre-treated with Interferons or Glatiramer Acetate. On the other hand, the ONWARD study has shown a significant reduction in ARR when comparing the pre-baseline treatment period with the Cladribine tablets treatment period. However, the study allowed all IFNs as pre-baseline treatments and pooled them together in the analysis. It was also not powered to detect differences in ARR and it did not include other first line treatments (DMF and Teriflunomide) in the analysis.

Here we want to evaluate the reduction in ARR afforded by Cladribine tablets, compared to the pre-baseline period, in patients treated with all first line drugs, who switch to Cladribine tablets according to the decision of their treating physician.

8 Research Question and Objectives

The main aim is to study in the real world setting the effectiveness of Cladribine tablets in terms of ARR and disability progression, in patients who switch from a first line drug (Interferons, Glatiramer Acetate, Teriflunomide, DMF).

8.1 Primary Objective

 To study the change in annualized relapse rate (ARR) in patients switching from first-line DMDs to Cladribine tablets, between the 12-month pre-baseline period and over the 12 months period before End of Study follow-up (2 years)

8.2 Secondary Objectives

- To assess change in annualized relapse rate (ARR) in patients switching from first-line DMDs to Cladribine tablets, between the 12-month pre-baseline period and over the 12 months period after initiation of Cladribine tablets (1 year)
- To assess disability progression. Disability progression is defined as progression on ≥1 of 3 components (EDSS, T25FW, and/or 9HPT) confirmed ≥24 weeks apart and with a ≥20% minimum threshold change for T25FW and 9HPT. T25FW and 9HPT are optional and will be performed if done as per routine practice. Progression on EDSS is defined as at least 1 point in the EDSS score or an increase of at least 1.5 points if the baseline EDSS score is 0.
- To assess disability improvement. Disability Improvement is defined as improvement on ≥1 of 3 components (EDSS, T25FW, and/or 9HPT) confirmed ≥24 weeks apart and with a ≥20% minimum threshold change for T25FW and 9HPT. T25FW and 9HPT are optional and will be performed if done as per routine practice. Improvement on EDSS is defined as a decrease in EDSS by at least 1 point (1.5 points if baseline EDSS was 1.5).
- To assess safety of Cladribine tablets in the real world, at two years
- To assess Quality of Life and treatment satisfaction
- To assess treatment adherence

-

Exploratory Objectives

- For those patients that the treating physicians decide to prescribe an MRI at baseline and/or Year 2:
 - 1. To compare MRI characteristics between baseline and Years 1 and 2
 - To compare MRI characteristics between the 12-month pre-baseline and postbaseline results (Years 1 and 2)
- To study effectiveness in 5 subgroups, defined according to the pre-baseline DMD treatment (IFN- B 1a / IFN- B 1 B / Glatiramer Acetate, Teriflunomide, DMF).

L04AA40 MS700568_0070	Cladribine	
9	Research Methods	
9.1	Study Design	
9.1.1	Design Overview	

This is a prospective, non-interventional, multicenter, Phase IV study in patients with a confirmed diagnosis of RRMS who switched from first-line DMD treatment (Interferons, Glatiramer Acetate, Teriflunomide, DMF) to treatment with Cladribine tablets in routine clinical practice.

No study specific interventions will be performed on the patients and there will not be any study specified visits. Assessments planned in this protocol will be according to clinical practice.

Patients will be enrolled consecutively at study sites in the participating countries. Each patient will be followed for the course of their standard Cladribine treatment (approximately 2 years according to clinical practice).

Figure 1 provides a schematic overview of the study design. Figure 2 provides an overview of the patient journey within the study. Enrolment may take place from the time of cladribine prescription up until the second treatment week, in the first treatment year.

[figure not shown]
[figure not shown]

Figure 1 - Schematic of Study Design³

³ Pts: patients: IFN: Interferon; DMF: Dymethyl fumarate; DMD: Disease Modifying Drug

* Interferon, Glatiramer Acetate, Teriflunomide, DMF

Figure 2 - Study Patient Journey

9.1.2 Outcomes

9.1.2.1 Primary

Difference in ARR between the pre-baseline 12-month period over the 12 months period before the End of Study follow-up (2 years)⁴.

9.1.2.2 Secondary

- Difference in ARR between the pre-baseline 12-month period and over the 12 months period after the start of cladribine (1 year)
- Percentage of patients with 6-month disability progression⁵ at the end of the study followup period (2 years), measured as EDSS, T25FW (optional) and 9-HPT (optional).

⁴ Relapses will be diagnosed by the treating physicians, as per routine clinical practice; a typical definition within this context is the appearance of new symptoms of the exacerbation of pre-existing symptoms that are attributed to MS and occur over a minimum of 24 hours and separated from a previous attack by at least 30 days, in the absence of fever or infection.

⁵ Disability progression is defined as progression on ≥1 of 3 components (EDSS, T25FW, and/or 9HPT) confirmed ≥24 weeks apart and with a ≥20% minimum threshold change for T25FW and 9HPT, Progression on EDSS is defined

L04AA40 MS700568 0070

Cladribine

- Percentage of patients with 6-month disability improvement⁴ at the end of the study followup period (2 years), measured as EDSS, T25FW (optional) and 9-HPT (optional)
- · Occurrence of adverse events and of serious adverse events
- Quality of life (MSIS-29)
- Treatment Satisfaction (TSQM v1.4)
- CCI
- Treatment adherence, assessed as percentage of cladribine tablets taken versus prescribed dose

9.1.2.3 Exploratory

- Number of MRI lesions (T2, T1 Gd+, CUA) at baseline and years 1 and 2
- Comparison of the number of MRI lesions (T2, T1 Gd+, CUA) between the pre-baseline 12 months and post-baseline results (years 1 and 2)
- An exploratory subgroup analysis will be conducted on effectiveness endpoints, with 5 groups defined according to the pre-baseline DMD treatment (IFN- β 1a / IFN- β 1 β / Glatiramer Acetate, Teriflunomide, DMF)

9.2 Setting

9.2.1 Study Population

The study population will be identified according to the below inclusion and exclusion criteria. For inclusion in the study, all of the following inclusion criteria must be fulfilled:

- Patients must voluntarily give written informed consent. Patients must read and fully understand the Informed Consent Form (ICF)
 - 2. Adult patients, males or females patients ≥ 18 years old.
 - Patients with confirmed diagnosis of Relapsing-Remitting Multiple Sclerosis (RRMS) diagnosed by the treating physician according to applicable clinical practice guidelines – (currently McDonald 2017 criteria), with high disease activity.

as at least 1 point in the EDSS score or an increase of at least 1.5 points if the baseline EDSS score is 0. Disability Improvement is defined as improvement on ≥ 1 of 3 components (EDSS, T25FW, and/or 9HPT) confirmed ≥ 24 weeks apart and with a $\ge 20\%$ minimum threshold change for T25FW and 9HPT. Improvement on EDSS is defined as a decrease in EDSS by at least 1 point (1.5 points if baseline EDSS was 1.5). T25FW and 9HPT are optional and will be performed if done as per routine practice.

- 4. Patients should have been treated with the same first-line DMD (Interferons, Glatiramer Acetate, Teriflunomide, DMF) and at a stable dose for at least one year prior to switch to Cladribine tablets and should have been prescribed Cladribine tablets, according to the decision of the treating physician, prior to enrollment in the study. Any washout period and/or washout methods required before switching (such as elimination of Teriflunomide) must have been conducted, according to the decision of the treating physician.
- 5. Required history data should be available:
 - MS data for the 12-months pre-baseline period (annualized relapse rate)
 - MS Medication History (prior DMDs)
- Fulfilment of the criteria for treatment with Cladribine tablets per standard of care in accordance with the local SmPC

Patients are not eligible for this study if they fulfill any of the following exclusion criteria:

- 1. Contraindications to use of cladribine tablets according to the Summary of Product Characteristics
- Patients with history of alcohol or drug abuse that could potentially interfere with their participation in the study.
- 3. Patient that have received Cladribine in the past
- Concurrent participation in an investigational study in which patient assessment and/or treatment may be dictated by a protocol.

9.2.2 Definition of Study Cohorts and Description of Treatments

This is a single cohort study enrolling all patients that switch to Cladribine tablets from first-line DMDs, according to the decision of the treating physician. Patients should have been under treatment with first-line DMDs for at least one year prior to switching (see Section 9.2.1) and should have been prescribed to Cladribine tablets prior to enrollment (baseline visit). Enrollment may take place from the time of cladribine prescription up until the second treatment week, in the first treatment year.

All eligible patients are treated with Cladribine tablets in routine clinical practice. Patients will receive Cladribine as per the SmPC and the discretion of their treating physician. According to the SmPC, each treatment course consists of 2 treatment weeks, one at the beginning of the first month and one at the beginning of the second month of the respective treatment year. Each treatment week consists of 4 or 5 days on which a patient receives 10 mg or 20 mg (one or two tablets) as a single daily dose, depending on body weight. If necessary, the treatment course in Year 2 can be delayed for up to 6 months to allow for recovery of lymphocytes (at least 800 cells/mm³). If this recovery takes more than 6 months, the patient should not receive Cladribine tablets anymore. In patients where cladribine tablet treatment was delayed, follow-up will remain 2 years after enrollment and will not be extended by the period by which treatment was delayed.

9.2.3 Observation Period

Each patient will be followed from the date the Informed Consent is signed until they are lost to follow-up, withdrawal of consent, death or the end of the data collection period, whichever comes first. Patients will be followed for 24 months from first dose of Cladribine. Follow-up will continue regardless of cladribine tablets discontinuation for 2 years after first dose or until withdrawal.

- MS Medication History: Disease modifying drug (DMD), immunosuppressive/immunomodulatory agents (other than DMD, such as corticosteroid treatment)
- Concomitant treatments
- Reason for switching from first line DMD to Cladribine tablets (clinical relapses or disability progression, new or enhancing MRI lesions, or other).
- · Date of start of therapy with Cladribine tablets and number of tablets taken
- Participation in a Cladribine Patient Support Program
- MS data History, including number of relapses within 12 months before initiation of Cladribine therapy and number of new/enlarged MRI lesions (T1 Gd+, T2 and CUA lesions) measured on the last MRI performed per clinical practice within the last 12 months before initiation of Cladribine therapy
- MSIS-29 Questionnaire: to be answered by the subject
- EQ-5D-3L Questionnaire: to be answered by the subject
- EDSS, T25FW, 9-HPT, T25FW and 9HPT are optional and will be performed if done as per routine practice.
- Safety recording and reporting
- Upon availability: MRI (T1 Gd+, T2 and CUA lesions). These assessments are not
 mandatory parts of this study; however, we kindly ask for providing the scores in case the
 tests were carried out due to medical reasons or as part of the clinical routine.

Cladribine

Visit 1 assessments (V1, indicative Month 6)

- · Total number of relapses while in study, up until this visit
- Date of administration of therapy with Cladribine tablets and number of tablets taken versus prescribed dose
- Concomitant treatments
- TSQM-v1.4 Questionnaire: to be answered by the subject
- EDSS, T25FW, 9-HPT, T25FW and 9HPT are optional and will be performed if done as per routine practice
- · Safety recording and reporting
- Upon availability: MRI (total number of T1 Gd+, T2 and CUA lesions). These assessments are not mandatory parts of this study; however, we kindly ask for providing the scores in case the tests were carried out due to medical reasons or as part of the clinical routine.

Visit 2 assessments (V2, indicative Month 12)

- Weight
- · Concomitant treatments
- Total number of relapses while in study, up until this visit
- Date of administration of therapy with Cladribine tablets and number of tablets taken versus prescribed dose
- TSQM-v1.4 Questionnaire: to be answered by the subject
- MSIS-29 Questionnaire: to be answered by the subject
- EQ-5D-3L Questionnaire: to be answered by the subject
- EDSS, T25FW, 9-HPT, T25FW and 9HPT are optional and will be performed if done as per routine practice.
- Safety recording and reporting
- Upon availability: and MRI (total number of T1 Gd+, T2 and CUA lesions). These
 assessments are not mandatory parts of this study however we kindly ask for providing the
 scores in case the tests were carried out due to medical reasons or as part of the clinical
 routine.

Visit 3 assessments (V3, indicative Month 18)

- · Total number of relapses while in study, up until this visit
- Date of administration of therapy with Cladribine tablets and number of tablets taken versus prescribed dose
- Concomitant treatments
- TSQM-v1.4 Questionnaire: to be answered by the subject

- EDSS, T25FW, 9-HPT, T25FW and 9HPT are optional and will be performed if done as per routine practice
- · Safety recording and reporting
- CC

Visit 4 assessments (V4, indicative Month 24)

- · Total number of relapses while in study, up until this visit
- Concomitant treatments
- . TSOM-v1.4 Questionnaire: to be answered by the subject
- · MSIS-29 Questionnaire: to be answered by the subject
- · EQ-5D-3L Questionnaire: to be answered by the subject
- EDSS, T25FW, 9-HPT, T25FW and 9HPT are optional and will be performed if done as per routine practice.
- · Safety recording and reporting
- CC

A patient is considered to have completed the study after they have had a follow-up visit at the end of the observation period of 24 months. Study termination earlier than month 24 may occur due to lost to follow up, informed consent withdrawal or any other reasons as recorded. Following assessments will be performed at study termination, if this information is available:

- Weight
- Total number of relapses while in study
- TSQM-v1.4 Questionnaire: to be answered by the subject
- MSIS-29 Questionnaire: to be answered by the subject
- CCI
- EDSS, T25FW, 9-HPT, T25FW and 9HPT are optional and will be performed if done as per routine practice.
- Safety recording and reporting
- Upon availability: MRI (total number of T1 Gd+, T2 and CUA lesions). These assessments
 are not mandatory parts of this study however we kindly ask for providing the scores in case
 the tests were carried out due to medical reasons or as part of the clinical routine.

For patients lost to follow up observations will be censored and will be handled as defined in the SAP. Lost-to follow-up is confirmed when at least 3 documented attempts to reach out the

Cladribine

patient have been made. If a subject is lost to follow-up, every possible effort must be made by study center personnel to contact the subject and determine the reason for discontinuation. The measures taken to follow-up must be documented. If a subject discontinues before completion of study procedures, the reason for discontinuation must be documented in the case report form (CRF) and source documents.

Safety data assessment

Safety events are collected throughout the study as described in Section 11.5.

9.2.5 Withdrawal from the Study

Patients may discontinue from the study at any time (withdraw consent). The reason for any study discontinuations will be collected, if available.

Patients who discontinue treatment will continue to be followed until end of follow-up period regardless of treatment status, unless they switch to another DMD treatment in which case they should be withdrawn from the study.

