11.4 Recording of Adverse Events

The recording period for AEs begins, when the subject is initially included in the study (date of signature of first informed consent) and continues at least end of the mandatory safety-follow-up period at last study visit. However, as enrollment may take place from the time of cladribine prescription up until the second treatment week, in the first treatment year, any ADRs assessed as related to cladribine by the Investigator after the first dose of cladribine but before signature of Informed Consent must be recorded in the eCRF as well.

All adverse events, as specified above, occurring during the study, must be documented by the Investigator in the eCRF, including its description, seriousness, severity (grading), duration (onset

and resolution dates), causal relationship, any other potential causal factors, actions taken with the study drug (e.g. dose reduction, withdrawal), required treatment and outcome of the AE.

Note - Event term 'Death', 'Disability' and 'Hospitalization'

Death, disability, and hospitalization are considered outcomes in the context of safety reporting and not usually considered ARs/AEs. Therefore the primary cause of death, disability or hospitalization should be recorded and reported as an SAE/AR, and the outcome should be recorded in a separate data field. However, a term for the outcome will be selected if it is the only information reported or provides significant clinical information.

If death occurs, the primary cause of death or event leading to death should be recorded and reported as an SAE. "Fatal" will be recorded as the OUTCOME of this respective event and not be as separate event. Only, if no cause of death can be reported (for example, sudden death, unexplained death), the death per se might then be reported as an SAE.

Reports of Special Situations (see definition) are also to be recorded in the CRF following the AE procedure, even if occurring without AE.

Pregnancy and Breastfeeding. Pregnancy or breastfeeding must be recorded in the CRF and additionally be reported to the Sponsor immediately (within 24 hours of awareness) by using separate paper data collection forms for pregnancy, independent if an AE was reported or not. The outcome of the pregnancy should be followed up and reported to the Sponsor until delivery.

Women who become pregnant under therapy with Cladribine tablets should discontinue treatment.

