## **9** General Specifications for Data Analyses

This section describes any general specifications not included in subsequent sections. This study is a single cohort study and no comparison between groups is planned. The "start date" for this study is the start date of treatment with Cladribine.

Continuous variables will be summarized using descriptive statistics, i.e. the number of patients with non-missing values (n), the number of patients with missing values (nmiss), mean, standard deviation (SD), median, 25th percentile (Q1) and 75th percentile (Q3), minimum, and maximum. If there are no missing values, the number of patients with missing values (nmiss) should be indicated by a 0. Mean, median, Q1, Q3, minimum and maximum will be reported with the same number of decimal places as collected in raw data while SD will be reported with one extra decimal place.

Qualitative variables will be summarized by frequency counts and percentages. Unless otherwise stated the calculation of proportions will be based on the number of patients of the analysis set of interest. Therefore, counts of missing observations will be included in the denominator and presented as a separate category.

The overall significance level is 5% two-sided. Confirmatory statistical tests will be performed on the primary outcome only. All other statistical tests mentioned in this IAP are to be regarded as exploratory. Exploratory statistical tests comparing study treatment groups will be performed two-sided. If confidence intervals (CIs) are to be calculated, these will be two-sided with a confidence probability of 95%, unless otherwise specified in this IAP.

In order to provide overall estimates of treatment effects, data will be pooled across sites. The "site" factor will not be considered in statistical models or for subgroup analyses due to the high number of participating sites in contrast to the anticipated small number of patients treated at each site.

All analyses will be performed using SAS® Software version 9.4 or higher. R version 3.2.2 or higher may be used to create some of the figures in case it provides a better alternative layout.

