## 9.6 End of Study, Date of last Contact and Lost to Follow-up

End of study is defined as the last visit performed by the patient within the period of 24-Months  $\pm$  3 months after baseline.

A patient will be considered lost to follow-up when he/she prematurely discontinued the study, meaning that he/she discontinued the study prior to finalizing the 24-Months observational period. As per the protocol and eCRF options, a patient can be lost to follow-up due to:

- Withdrew consent from study
- Death
- Change to other DMD
- Other reason (e.g. not able to contact the patient)

As per the study design, discontinuation of treatment does not imply lost to follow-up. Patients who discontinue the treatment will continue to be followed for safety reasons until the 24-Months observational period ends or unless they switch to another DMD treatment.

The date of the last contact will be derived as:

- End of study date, for patients completing the observational period
- Date of death for patients lost to follow-up due to death
- Maximum of the following event dates, when complete dates available, for lost to follow-up patients when lost to follow-up cause is not death:
  - o Maximum available date of visit.
  - Study drug start
  - o Adverse Event (AE) start and end dates
  - o Concomitant Medication (CM) start and end dates
  - o Date of Quality of Life (QoL) questionnaires (MSIS-29, CCI and Treatment Satisfaction Questionnaire for Medication [TSQM]).

Only dates associated with patient actual examinations reported in the eCRF will be used in the derivation. Dates associated with a technical operation unrelated to patient status such as the date a blood sample was processed will not be used.

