#### 9.7 Definition of On-treatment Period

The on-treatment period is defined as the date of the first dose of study treatment to the date of the last contact. Due to the posology and long-term effects of Cladribine, a patient is on-treatment from the first dose received of Cladribine until the follow-up period ends.

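### New adverse events after a switch to another DMD are not captured, yet switchers stay in the denominator of crude safety percentages, which may therefore understate two-year incidence by an unknown amount

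*Protocol*

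**What the plan says.** **Follow-up.** Protocol 9.2.3 sets 24 months from first dose: "Follow-up will continue regardless of cladribine tablets discontinuation for 2 years after first dose or until withdrawal". Protocol 9.2.5 makes one exception for patients who stop cladribine: they remain in follow-up "unless they switch to another DMD treatment in which case they should be withdrawn from the study". SAP 9.6 repeats this for safety. Such patients are "followed for safety reasons until the 24-Months observational period ends or unless they switch to another DMD treatment", and "Change to other DMD" is listed among the reasons for loss to follow-up.

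**Recording.** Under Protocol 11.4, AE recording starts at consent and "continues at least end of the mandatory safety-follow-up period at last study visit". Protocol 9.2.4 includes safety recording at early study termination where the information is available. Protocol 11.5 has recorded SAEs, ADRs and AESIs followed until they stabilise or the outcome is known, and pregnancies followed even after withdrawal.

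**Objective and analysis.** A secondary objective is "To assess safety of Cladribine tablets in the real world, at two years" (Protocol 8.2). SAP 15 and 15.1 summarise treatment-emergent events in the FAS as numbers and percentages of patients, in tables titled as incidence. SAP 9 fixes the denominator: "Unless otherwise stated the calculation of proportions will be based on the number of patients of the analysis set of interest". SAP 15 plans no person-time rate, no cumulative-incidence estimate and no safety sensitivity analysis for early withdrawal. SAP 10.1 already derives length of follow-up for each FAS patient.

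**The concern.** A patient who stops cladribine and takes nothing else is observed to month 24. A patient who stops and starts another DMD leaves the study. A first severe infection, malignancy or severe lymphopenia in the second patient after leaving cannot enter a numerator, but the patient remains in the denominator. Someone withdrawn event-free at month 8 is counted exactly like someone observed event-free for 24 months.

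Protocol 9.2.4 says that observations of patients lost to follow-up will be censored and handled as the SAP defines. For the safety tables the SAP defines no such handling. At stake is how the safety percentages are read: with a two-year objective, a reader will naturally take them as two-year risks in treated patients. The relapse analysis is a separate matter.

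**Working it through.** There is no figure in the plan to reproduce. The readable text gives no AESI rate, switch rate or dropout rate.

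**Step 1: direction.** Switchers stay in the FAS denominator (SAP 9, SAP 15). First events after the switch have no route into the numerator (Protocol 9.2.5 and 11.4, SAP 9.6). The crude percentage is therefore at or below the 24-month incidence in all treated patients. It is strictly below only if some switcher has a first event between the switch and month 24.

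**Step 2: observation time lost.** Inputs are N = 242 (Protocol 9.5, taking all as treated) and 24 months (Protocol 9.2.3), so at most 242 × 2 = 484 patient-years. The switch fraction s and switch month t are assumptions. The share lost is s × (24 − t)/24.

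- s = 5%, t = 18: 0.05 × 6/24 = 1.25%, or 6.1 patient-years.
- s = 10%, t = 12: 0.10 × 12/24 = 5.0%, or 24.2 patient-years.
- s = 20%, t = 6: 0.20 × 18/24 = 15%, or 72.6 patient-years.

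**Step 3: effect on a crude percentage.** Assume a constant hazard. Let R be the two-year risk in non-switchers, h = −ln(1 − R)/24 per month, and m the hazard multiplier in switchers.

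- Observed = (1 − s)R + s(1 − exp(−h·m·t))
- Full 24 months = (1 − s)R + s(1 − exp(−24·h·m))

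For R = 10%, h = 0.10536/24 = 0.00439.

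| R | s | t | m | Full | Observed | Gap (points) | Relative | Patients of 242 |
|---|---|---|---|---|---|---|---|---|
| 10% | 10% | 12 | 1 | 10.00% | 9.51% | 0.49 | 4.9% | 1.2 |
| 10% | 10% | 12 | 2 | 10.90% | 10.00% | 0.90 | 8.3% | 2.2 |
| 2% | 5% | 18 | 1 | 2.00% | 1.98% | 0.02 | 1.2% | 0.06 |
| 25% | 20% | 6 | 1 | 25.0% | 21.4% | 3.6 | 14.4% | 8.7 |
| 2% | 20% | 6 | 3 | 2.78% | 1.90% | 0.88 | 31.5% | 2.1 |

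Over s = 5–20%, t = 6–18 and R = 2–25% with m = 1, the relative gap runs from about 1% to 15%.

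**Step 4: what a patient-year rate repairs.** Take R = 10%, s = 10%, t = 12. The yearly hazard in non-switchers is 0.10536/2 = 0.05268.

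- With m = 1, the rate is 5.27 per 100 patient-years with or without the withdrawals.
- With m = 2, non-switchers give 217.8 × 0.10 = 21.78 events over 21.78/0.05268 = 413.4 patient-years. The 24.2 switchers give 4.598 events over 4.598/0.10536 = 43.6 patient-years if followed to month 24, or 2.42 events over 2.42/0.10536 = 23.0 patient-years if withdrawn at month 12.
- The full rate is 26.378/457.1 = 5.77. The observed rate is 24.20/436.4 = 5.55, about 3.9% low, against 8.3% for the crude percentage.

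Person-time thus removes the shortfall when switching is unrelated to risk, and only part of it otherwise.

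**The case against.** The strongest reply is that the rule is deliberate and consistent. A reader might infer a contradiction with SAP 9.7, which says "Due to the posology and long-term effects of Cladribine, a patient is on-treatment from the first dose". But the same section ends the on-treatment period at last contact, SAP 9.6 names a DMD change as a reason that follow-up ends, and Protocol 9.2.3 allows for withdrawal. Protocol 9.2.3 does not list a switch among its end points, which could be tidied, but the sections do not conflict. Limiting cladribine safety to the time before another DMD is a defensible target, since later events are confounded by the new drug.

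A reader might also infer that all safety recording stops at the switch. It does not: Protocol 11.4 sets a minimum, safety is recorded at termination where available, recorded events are followed to outcome and pregnancies beyond withdrawal. Only new onsets other than pregnancy are lost.

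Two further inferences lack support in the documents: that the AESIs are typically delayed, and that patients switch because of poor response or intolerance. Neither is stated.

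It also counts for the plan that safety is descriptive, that SAP 10.1 shows length of follow-up and reasons for discontinuation, and that Protocol 9.9 admits bias from attrition. Truncation will be visible. What remains is that a crude FAS percentage estimates neither target: not two-year incidence in treated patients, because follow-up is cut, and not incidence before any new DMD, because time at risk is ignored.

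**Conclusion.** The point holds as a limited one. New AE and AESI onsets after a DMD switch are not captured, while switchers remain in the denominator, so the crude percentages may understate two-year incidence in treated patients. To say that they are understated would go further than the documents allow: that needs at least one switcher with a first event after withdrawal, and neither number is known. The illustrative gap of about 1–15% relative (0.02 to 3.6 points) rests on assumed switch rates, timings and risks, a constant hazard, and equal risk in switchers. Larger gaps need switchers to be at higher risk. This is an inexpensive improvement to the analysis and labelling, with better data collection as a further option. It concerns data collection and analysis only, not treatment decisions.

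**What to change.** **SAP change (low cost).** In SAP 15.1, for AESIs and SAEs, add incidence per 100 patient-years, counting time from first dose to first event or last contact with the follow-up length derived in SAP 10.1, or give a cumulative-incidence estimate. SAP 9.6 lets AE and medication end dates extend last contact, so check that these do not lengthen a switcher's time at risk past withdrawal. Label the crude percentages as covering follow-up only up to any DMD switch. State that person-time does not remove bias if switching is related to event risk. The cost is SAP wording and a few tables; no new data are needed.

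**Protocol change (where an amendment is feasible).** Change 9.2.5 so that after a switch the new DMD and its start date are recorded, and SAEs, AESIs and ADRs continue to be recorded from routine visits to month 24 unless consent is withdrawn. Tabulate onsets before and after the new DMD separately. The cost is an amendment with ethics review, possibly revised patient information, and an eCRF change, because the eCRF now treats a switch as study exit. Patients already withdrawn could not be captured uniformly, and post-switch events would be confounded by the new DMD, which is why they are shown separately.
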